## **4.3. Sample Size and Power**

### **4.3.1. Part 1C-1, Homologous Booster Dose**

All participants enrolled in Part 1A or Part 1B who meet the eligibility criteria for BD will be offered a BD of mRNA-1273 50  $\mu$ g. With more than 1,000 participants expected to

receive mRNA-1273 BD, the study Part 1C-1 (Homologous Booster Dose) has a 90% probability to observe at least 1 participant with an AE at a true AE rate of 0.25%.

Serum samples from all participants will be collected and banked, a subset of participants will be selected, and their samples will be processed for immunogenicity testing (the Immunogenicity Subset) at specified timepoints.

Approximately 362 participants who receive mRNA-1273 BD will be selected for the Immunogenicity Subset for Part 1C-1, with a target of 289 participants receiving mRNA-1273 BD in the PP Immunogenicity Subset for Part 1C-1 (adjusting for approximately 20% of participants who may be excluded from the PP Immunogenicity Subset, as they may not have immunogenicity results due to any reason or may have protocol deviations impacting critical data).

For the primary immunogenicity objective in Part 1C-1, noninferiority tests of two null hypotheses based on two coprimary endpoints, respectively, will be performed. The sample size calculation for each of the two noninferiority tests was performed, and the larger sample size was chosen for the study.

- With approximately 289 participants receiving mRNA-1273 BD in the PP Immunogenicity Subset in Study P203 Part 1C-1 and 289 participants in the PP Immunogenicity Subset in young adults (18-25 years of age) in Study P301, there will be 90% power to demonstrate noninferiority of the immune response post BD as measured by Ab GM in adolescents in Study P203 Part 1C-1 compared with that in young adults (18-25 years of age) following primary series of mRNA-1273 in Study P301, at a 2-sided alpha of 0.05, assuming an underlying GMR value of 1, a noninferiority margin of 1.5, and a point estimate minimum threshold of 0.8. The standard deviation (SD) of the log-transformed levels is assumed to be 1.5.
- With approximately 289 participants receiving mRNA-1273 BD in the PP Immunogenicity Subset in Study P203 Part 1C-1 and 289 participants in the PP Immunogenicity Subset in young adults (18-25 years of age) in Study P301, there will be at least 90% power to demonstrate noninferiority of the immune response post BD as measured by seroresponse rate in adolescents in Study P203 Part 1C-1 compared with that in young adults (18-25 years of age) following primary series of mRNA-1273 in Study P301, at a 2-sided alpha of 0.05, assuming a true seroresponse rate of 90% in young adults (18-25 years of age) following primary series of mRNA-1273 in Study P301, and a true seroresponse rate of 90% post BD

in adolescents in P203 Part 1C-1 (i.e., true rate difference is 0 compared to young adults [18-25 years of age] in Study P301), and a noninferiority margin of 10%.

#### **4.3.2. Part 1C-2, Heterologous Booster Dose**

Approximately 362 participants who received non-Moderna COVID-19 vaccine as primary series vaccination at least 3 months prior were planned to be enrolled to receive mRNA-1273 50 µg as heterologous booster in Part 1C-2. However, the study population in Part 1C-2 will have less than the planned number participants enrolled, as a result of slow enrollment and discontinuation of recruitment in Part 1C-2 (Protocol Section 3.1.1.4).

#### **4.3.3. Part 2**

Approximately 362 participants were planned to be enrolled to receive mRNA-1273 50 µg in the open label Part 2. However, the study population in Part 2 will have less than the planned number of participants receiving at least one dose of 50 µg mRNA-1273, with a small sample size as a result of slow enrollment and discontinuation of recruitment in Part 2 (Protocol Section 3.1.2).

#### **4.3.4. Part 3**

With at least 300 adolescents enrolled in Part 3 to receive 50 µg mRNA-1273.222, the study will have at least a 95% probability to observe at least 1 participant with an AE at a true AE rate of 1%.

Assuming a true serum Ab GMR of 1.6 for GM value against Omicron BA.4/BA.5 at Day 29 after Dose 1 of mRNA 1273.222 in baseline SARS-CoV-2 positive adolescents compared with GM value against Omicron BA.4/BA.5 at Day 57 after Dose 2 of mRNA-1273 primary series in young adults who are baseline SARS-CoV-2 negative in P301, with approximately 168 participants in the PP immunogenicity subset who are baseline SARS-CoV-2 positive in P203 Part 3 and 300 young adults in P301 who are baseline SARS-CoV-2 negative, there will be at least >90% power to demonstrate superiority of the serum Ab GM value against Omicron BA.4/BA.5 after Dose 1 of mRNA-1273.222 in adolescents in P203 to that after Dose 2 of mRNA-1273 in young adults in Study P301 at two-sided  $\alpha$  of 0.05 using a superiority margin of 1.0. The standard deviation of the natural log transformed levels of Ab is assumed to be 1.5.

Assuming a true serum Ab GMR of 1.1 for GM value against ancestral strain at Day 29 after Dose 1 of mRNA 1273.222 in baseline SARS-CoV-2 positive adolescents compared with GM value against ancestral strain at Day 57 after Dose 2 of mRNA-1273 primary

series in young adults who are baseline SARS-CoV-2 negative in P301, this sample size will also provide at least >90% power to demonstrate noninferiority of GM value of Ab against ancestral strain at Day 29 post Dose 1 of mRNA-1273.222 in adolescents in P203 to that after Dose 2 of mRNA-1273 in young adults in Study P301 at two-sided  $\alpha$  of 0.05 using a noninferiority margin of 1.5. The standard deviation of the natural log transformed levels of Ab is assumed to be 1.5.

With approximately 30% of participants in Part 3 who may be excluded from the PP Immunogenicity Subset-baseline SARS-CoV-2 positive (PPIS-POS), as they may be baseline SARS-CoV-2 negative or have missing immunogenicity results due to any reason or protocol deviations impacting critical data, approximately 240 participants are required in Part 3 to provide 168 participants in the PP Immunogenicity Subset-baseline SARS-CoV-2 positive.

#### **4.4. Multiplicity Adjustment**

A hierarchical sequential hypothesis testing (fixed-sequence) method will be used to adjust multiplicity to preserve the family-wise Type I error rate ( $\alpha = 0.05$ ). The hypothesis testing for the 2 coprimary endpoints (geometric mean titer [GMT] and SRR) for the primary series of mRNA-1273 in Part 1A was completed and statistically significant based on data snapshot dated 08 May 2021, and thus the  $\alpha$  level of 0.05 can be passed to Part 1C-1 hypothesis testing. In Part 1C-1 Homologous Booster Phase, the hypothesis testing for the 2 coprimary endpoints (GMT and SRR against the ancestral strain) after BD of mRNA-1273 will be tested first at  $\alpha$  level of 0.05. The testing in Part 1A and 1C-1 will continue through the sequence only until an endpoint is not statistically significant (did not meet specified noninferiority success criteria), in which case the testing will stop. If the hypothesis testing for the 2 coprimary endpoints in Part 1C-1-Homologous Booster Phase is statistically significant (meeting the noninferiority success criteria of the coprimary endpoints), the  $\alpha$  level of 0.05 will be passed to the hypothesis testing in Part 3.

For the key secondary objective in Part 1C-1 Homologous Booster Phase to evaluate immune response elicited by the 50  $\mu$ g prototype booster of mRNA-1273 against variant(s) of interest, the key secondary endpoints will be analyzed independently, given that prototype vaccine mRNA-1273 does not contain variant specific sequences.

### **Part 3**

Since the hypothesis testing for the coprimary endpoints in Part 1C-1 was statistically significant based on an IA with a data cutoff dated 16 May 2022, the  $\alpha$  level of 0.05 (two-sided) was passed to Part 3 hypothesis testing.

#### **4.5. Blinding and Unblinding**

Not applicable.

### **5. Analysis Populations**

The following analysis sets are defined: Full Analysis Set (FAS), Immunogenicity Subset, Per-protocol (PP) Immunogenicity Subset, Per-protocol (PP) Immunogenicity Subset - Pre-booster SARS-CoV-2 Negative for Part 1C-1, Modified Intent-to-Treat-1 (mITT1) Set, Solicited Safety Set (not applicable to Part 1B), and Safety Set.

#### **5.1. Full Analysis Set**

##### The Full Analysis Set (FAS) (Long-term Analysis)

The FAS (Long-term Analysis) consists of FAS (Part 1B, Open-Label Phase) for Placebo-mRNA-1273 cohort and FAS for mRNA-1273 cohort. FAS (Part 1B, Open-Label Phase) for Placebo-mRNA-1273 cohort consists of all participants from Part 1A placebo group who cross over and receive mRNA-1273 in Part 1B. FAS for mRNA-1273 cohort is same as the FAS in Part 1A. Participants will be analyzed in the mRNA-1273 group or placebo-mRNA-1273 group if applicable.

##### The Full Analysis Set (FAS) (Part 1C-1, Part 1C-2)

The FAS for Part 1C-1 and Part 1C-2 consists of all participants who received at least one booster dose in each part. Participants will be analyzed according to the treatment group assigned.

##### The Full Analysis Set (FAS) (Part 2, Part 3)

The FAS for Part 2 and Part 3 consists of all participants who received at least one dose of IP in each part. Participants will be analyzed according to the treatment group assigned.

#### **5.2. Immunogenicity Subset**

##### Immunogenicity Subset (Long-term Analysis at Day 1, Day 57, and Day 209)

Immunogenicity Subset for long-term analysis at Day 1, Day 57 and Day 209 consists of a) participants selected for immune testing (Section 6.4.1), and

- b) have baseline (pre-dose 1) SARS-CoV-2 status available, and
- c) have baseline (pre-dose 1) and at least one post-injection antibody assessment for the analysis endpoint.

Immunogenicity Subset (Part 1C-1, Homologous Booster Dose)

Immunogenicity Subset for Part 1C-1 homologous booster dose consists of

- a) participants selected for immune testing (Section 6.4.1), and
- b) have baseline (pre-dose 1) SARS-CoV-2 status available, and
- c) have at least one post-booster antibody assessment for the analysis endpoint.

Immunogenicity Subset (Part 1C-2, Heterologous Booster Dose)

Immunogenicity Subset for Part 1C-2 Heterologous booster dose consists of all participants who have at least one post-booster antibody assessment for the analysis endpoint.

Immunogenicity Subset (Part 2)

Immunogenicity Subset for Part 2 consists of all participants who have baseline (pre-dose 1) and at least one post-injection antibody assessment for the analysis endpoint.

Immunogenicity Subset (Part 3)

Immunogenicity Subset for Part 3 consists of all participants who have baseline (pre-dose 1) and at least one post-injection antibody assessment.

**5.3. Per-protocol (PP) Immunogenicity Subset**

**Per-protocol (PP) Immunogenicity Subset (Long-term Analysis at Day 1, Day 57 and Day 209)**

Per-Protocol (PP) Immunogenicity Subset (Long-term Analysis) consists of all participants in Immunogenicity Subset (Long-term Analysis) who meet all the following criteria:

- a) Received planned doses of study vaccination per schedule
- b) Complied with the timing of second dose of injection
- c) Had a negative SARS-CoV-2 status at baseline (pre-dose 1)
- d) Had no major protocol deviations that impact key or critical data

The PP Immunogenicity Subset (Long-term Analysis) will serve as the population for the long-term analysis of immunogenicity data.

### **Per-protocol (PP) Immunogenicity Subset (Part 1C-1, Homologous Booster Dose)**

Per-Protocol (PP) Immunogenicity Subset (Part 1C-1) consists of all participants in Immunogenicity Subset for Part 1C-1 who meet all the following criteria:

- a) Received 2 doses of mRNA-1273 in Part 1A per schedule
- b) Received booster dose in Part 1C-1
- c) Had a negative SAS-CoV-2 status at baseline (pre-dose 1 of Part 1A)
- d) Had BD-Day 29 Ab assessment for the analysis endpoint
- e) Had no major protocol deviations that impact key or critical data
- f) Not receive off-study COVID-19 vaccination prior to BD-Day 29 visit

### **Per-protocol (PP) Immunogenicity Subset - Pre-booster SARS-CoV-2 Negative (Part 1C-1, Homologous Booster Dose)**

PP Immunogenicity Subset - Pre-booster SARS-CoV-2 Negative for Part 1C-1 consists of participants who are in PP Immunogenicity Subset (Part 1C-1, Homologous Booster Dose), and are pre-booster SARS-CoV-2 negative, defined as no virologic or serologic evidence of SARS-CoV-2 infection on or before BD-Day 1 (pre-booster), i.e. RT-PCR result is not positive if available at BD-Day 1 and a negative bAb specific to SARS-CoV-2 nucleocapsid (as measured by Roche Elecsys Anti-SARS-CoV-2 assay) on or before BD-Day 1 .

PP Immunogenicity Subset - Pre-booster SARS-CoV-2 Negative for Part 1C-1 will serve as the population for the primary and key secondary analysis of immunogenicity data in Part 1C-1. The PP Immunogenicity Subset for Part 1C-1 will serve as the population for the analysis of immunogenicity in Part 1C-1 by pre-booster SARS-CoV-2 status (negative vs. positive).

### **Per-protocol (PP) Immunogenicity Subset (Part 1C-2, Heterologous Booster Dose)**

Per-Protocol (PP) Immunogenicity Subset (Part 1C-2) consists of all participants in Immunogenicity Subset for Part 1C-2 who meet all the following criteria:

- a) Received booster dose in Part 1C-2
- b) Had BD-Day 29 Ab assessment for the analysis endpoint

- c) Had no major protocol deviations that impact key or critical data
- d) Not receive off-study COVID-19 vaccination prior to BD-Day 29 visit

The PP Immunogenicity Subset for Part 1C-2 will serve as the population for the analysis of immunogenicity in Part 1C-2 by pre-booster SARS-CoV-2 status (negative vs. positive).

### **Per-protocol (PP) Immunogenicity Subset (Part 2)**

Per-Protocol (PP) Immunogenicity Subset (Part 2) consists of all participants in Immunogenicity Subset (Part 2) who meet all the following criteria:

- a) Received at least one dose of planned injection
- b) Had Day 29 Ab assessment for the analysis endpoint
- c) Had no major protocol deviations that impact key or critical data

### **Per-protocol (PP) Immunogenicity Subset - Baseline SARS-CoV-2 Positive (Part 2)**

Per-Protocol (PP) Immunogenicity Subset - Baseline SARS-CoV-2 Positive (Part 2), abbreviated as PPIS-POS (Part2), consists of all participants in Per-protocol Immunogenicity Subset (Part 2) who had serologic or virologic evidence of SARS-CoV-2 infection at baseline.

The PP Immunogenicity Subset – Baseline SARS-CoV-2 Positive (Part 2) will serve as the population for the analysis of immunogenicity data in Part 2.

### **Per-protocol (PP) Immunogenicity Subset (Part 3)**

Per-Protocol (PP) Immunogenicity Subset (Part 3) consists of all participants in Immunogenicity Subset (Part 3) who meet all the following criteria:

- a) Received planned doses of study vaccination per schedule
- b) Had Day 29 Ab assessment for the analysis endpoint
- c) Had no major protocol deviations that impact key or critical data
- d) Not receive off-study COVID-19 vaccination prior to Day 29 visit

### **PP Immunogenicity Subset - Baseline SARS-CoV-2 Postive (Part 3)**

PP Immunogenicity Subset - Baseline SARS-CoV-2 Postive (Part 3) consisting of all participants in PP Immunogenicity Subset (Part 3) and who have serologic and/or virologic evidence of SARS-CoV-2 infection at baseline, will serve as the population for the primary and secondary analysis of immunogenicity data in Part 3. Per-protocol (PP) Immunogenicity

Subset (Part 3) will serve as the population for the analysis of immunogenicity by baseline SARS-CoV-2 status (negative vs. positive).

#### **5.4. Modified Intent-to-Treat-1 (mITT1) Set**

##### mITT1 Set (Long-term Analysis)

The mITT1 Set (Long-term Analysis) consists of mITT1 Set (Part 1B, Open-Label Phase) for Placebo-mRNA-1273 cohort and mITT1 Set for mRNA-1273 cohort. mITT1 Set (Part 1B, Open-Label Phase) for placebo-mRNA-1273 cohort consists of all cross-over participants in the FAS (Part 1B, Open-Label Phase) who had no serologic or virologic evidence of prior SARS-CoV-2 infection (both negative RT-PCR test for SARS-CoV-2 and negative serology test based on bAb specific to SARS-CoV-2 nucleocapsid) before the first dose of mRNA-1273 in Part 1B and received at least one dose of mRNA-1273 without wrong treatment, i.e., all FAS cross-over participants excluding those with positive or missing RT-PCR test or serology test prior to the first dose of mRNA-1273 and those who received the wrong treatment in Part 1B (i.e., at least one dose received in Part 1B is not as assigned). The mITT1 Set for mRNA-1273 cohort is same as the mITT1 Set in Part 1A.

##### mITT1 Set (Part 1C-1, Homologous Booster Dose)

The mITT1 Set for Part 1C-1 consists of all participants in the FAS for Part 1C-1 who had no serologic or virologic evidence of prior SARS-CoV-2 infection (both negative RT-PCR test for SARS-CoV-2 and negative serology test based on bAb specific to SARS-CoV-2 nucleocapsid) pre-booster dose and received one booster dose without wrong treatment, i.e., all FAS participants excluding those with pre-booster positive or missing RT-PCR test or serology test and those who received the wrong booster dose (i.e., dose received in Part 1C-1 is not as assigned).

Participants will be analyzed according to their treatment group (mRNA-1273-Booster, or Placebo-mRNA-1273-Booster).

#### **5.5. Solicited Safety Set**

##### Solicited Safety Set (Part 1C-1, Part 1C-2, Part 2 and Part 3)

The Solicited Safety Set consists of all participants who received any injection of IP in each part, and contribute any solicited AR data post injection. The Solicited Safety Set will be used for the analyses of solicited ARs in each part. Participants will be analyzed according to the treatment groups received. In addition, the following Solicited Safety Set

is defined for each injection separately for Part 2 and Part 3. The First (Second) Injection Solicited Safety Set consists of all subjects in the Solicited Safety Set who have received the first (second) study injection and have contributed any solicited AR data from the time of first (second) study injection through the following 6 days.

## 5.6. Safety Set

### Safety Set (Long-term Analysis)

The Safety Set (Long-term Analysis) consists of Safety Set (Part 1B, Open-Label Phase) for Placebo-mRNA-1273 cohort and Safety Set for mRNA-1273 cohort. Safety Set (Part 1B, Open-Label Phase) consists of all participants from Part 1A placebo group who cross over and receive mRNA-1273 in Part 1B. The Safety Set for Long-term Analysis for mRNA-1273 cohort is same as the Safety Set in Part 1A. The Safety Set will be used for analysis of safety except for the solicited ARs. Participants will be analyzed in the mRNA-1273 group or Placebo-mRNA-1273 group.

### Safety Set (Part 1C-1, Part 1C-2, Part 2 and Part 3)

The Safety Set for Part 1C-1, Part 1C-2, Part 2 and Part 3 consists of all participants who received any study injection of IP in each part. The Safety Set will be used for analysis of safety except for the solicited ARs. Participants will be analyzed according to the treatment group received. In addition, following safety set is defined for Part 3. The Second Injection Safety Set for Part 3 consists of all participants who received the second injection of IP in Part 3.

## 6. Statistical Analysis

### 6.1. General Considerations

The Schedule of Assessments for each part is provided in SAP for Part 1A.

**Continuous variables** will be summarized using the following descriptive summary statistics: the number of subjects (n), mean, standard deviation (SD), median, minimum (min), and maximum (max).

**Categorical variables** will be summarized using counts and percentages.

### Baseline Value for Each Part

- **Value of pre-first dose of mRNA-1273 for Part 1B**, unless specified otherwise, is defined as the most recent non-missing measurement (scheduled or unscheduled) collected before the first dose of mRNA-1273 in Part 1B.
- **Pre-booster value for Part 1C-1, and Part 1C-2**, unless specified otherwise, is defined as the most recent non-missing measurement (scheduled or unscheduled) collected before the booster dose. For immunogenicity tests, the pre-booster is defined as the most recent non-missing measurement (scheduled or unscheduled) collected before or on the date of booster dose.
- **Baseline value for Part 2 and Part 3** is defined using the same approach as Part 1A.

For the summary statistics of all numerical variables unless otherwise specified, the display precision will follow programming standards. Please see [Appendix A](#) for variable display standards.

When count data are presented, the percentage will be suppressed when the count is zero in order to draw attention to the non-zero counts. A row denoted “Missing” will be included in count tabulations where specified on the shells to account for dropouts and missing values. The denominator for all percentages will be the number of subjects in that vaccination group within the analysis set of interest, unless otherwise specified.

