- a) study day prior to the booster dose will be calculated as: date of assessment/event – date of the booster injection;
- b) study day on or after the date of the booster dose will be calculated as: date of assessment/event – date of the booster injection + 1;

**Study day relative to the most recent** injection will be calculated as below:

- a) study day on or after the date of the first injection (if applicable) but before the second injection (if applicable) will be calculated as: date of assessment/event – date of the first injection + 1;
- b) study day on or after the date of the second injection (if applicable) but before the booster injection (if applicable) will be calculated as: date of assessment/event – date of the second injection + 1;
- c) study day on or after the date of booster dose in Part 1C-1 (if applicable), Part 1C-2 or Part 2 (for participants who receive booster dose) will be calculated as: date of assessment/event – date of the booster injection + 1;  
if study day is on the same day as the injection, date and time will be compared with the injection date and time.

**For calculation regarding antibody levels/titers**, antibody values reported as below LLOQ will be replaced by  $0.5 \times \text{LLOQ}$ . Values that are greater than the upper limit of quantification (ULOQ) and without actual values reported (eg, '>xxx') will be converted to the ULOQ. Values that are greater than the ULOQ and with actual values reported will not be imputed (i.e. actual values will be used). Missing results will not be imputed.

The following **analysis periods for safety analyses** will be used as applicable for specific subjects cohort in this study:

- Up to 28 days after vaccination: this stage starts at the day of each vaccination and continue through the earliest date of (the day of each vaccination and 27 subsequent days, next vaccination [if applicable]). This analysis period will be used as the primary analysis period for safety analyses including unsolicited AE, except for solicited AR, unless specified otherwise.
- Overall period or throughout the study: this analysis period starts at the first injection on Day 1 and continues through the earliest date of (study completion, discontinuation from the study, or death).

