##### Sampling Plan

The first ~400 participants in the mRNA-1273 group who received booster dose (third dose, starting from 27Dec2021) in Part 1C-1 and meet all the criteria below will be selected for the immunogenicity subset.

- The participant is in Full Analysis Set (Part 1C-1, Homologous Booster Dose).
- SARS-CoV-2 status is not missing for baseline (pre-dose 1).

The blood samples of these subjects collected at the long-term timepoints (Day 1, Day 57, and Day 209) and subsequent booster dose phase timepoints (BD-Day 1 and BD-Day 29) will have immunogenicity testing, to support both the long-term immunogenicity analysis and booster dose immunogenicity analysis.

The target is to obtain 289 participants in the PP Immunogenicity Subset with pre-booster negative SAR-CoV-2 status (adjusting for approximately 25% of participants who may be excluded as they may have pre-booster positive SAR-CoV-2 status, or have no immunogenicity results due to any reason).

For the noninferiority tests of Ab GM and seroresponse rate at BD-Day 29 in adolescents in Study P203 compared with the primary series GM at Day 57 in young adults (18-25 years of age) in Study P301 receiving mRNA-1273, an immunogenicity subset of 340 young adults in Study P301 randomly selected from all participants (18-25 years of age) receiving mRNA-1273 will be used, with a target of 289 participants in the PP Immunogenicity Subset (using same definition as in Study P203) after adjusting for

approximately 15% of participants not meeting inclusion criteria for PP Immunogenicity Subset.

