#### **6.4.6. Exploratory Analysis of Antibody-Mediated Immunogenicity Endpoints**

For each group applicable, the following evaluations will be performed at each time point at which blood samples are collected for immunogenicity antibody tests against SAS-CoV-2 prototype or variants of interest as applicable.

- GM level of SARS-CoV-2-specific Ab levels with corresponding 95% CI will be provided at each time point (e.g., Baseline [Pre-dose 1], Day 29, Day 57, Day 209, Pre-booster, and BD-Day 29). The 95% CIs will be calculated based on the t-distribution of the log-transformed values then back transformed to the original scale for presentation. GM level will be plotted at each timepoint using boxplot. The following descriptive statistics will be also provided at each time point: the number of subjects (n), median, minimum and maximum.
- GM fold-rise of SARS-CoV-2-specific Ab levels with corresponding 95% CI will be provided at each timepoint over baseline (pre-dose 1) level, and post-booster timepoint over pre-dose 1 level and pre-booster level (Part 1C only). The 95% CIs will be calculated based on the t-distribution of the log-transformed values then back transformed to the original scale for presentation. The following descriptive statistics will be also provided at each time point: the number of subjects (n), median, minimum and maximum.

Proportion of subjects with fold-rise  $\geq 2$  of serum SARS-CoV-2 specific Ab levels from pre-dose 1 and pre-booster (Part 1C only) if applicable at each time point will be tabulated with 2-sided 95% Clopper-Pearson CIs.

- Proportion of subjects with seroresponse due to vaccination relative to pre-dose 1 will be tabulated with 2-sided 95% Clopper-Pearson CIs at each timepoint.
- For Part 1C-1, An analysis of covariance (ANCOVA) model may be performed to assess the difference in the post-booster GMT or GM values at BD-Day 29 in

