### 8.2. Appendix B Analysis Visit Windows for Safety and Immunogenicity Analysis

Safety and Immunogenicity Analysis will be summarized using the following analysis visit window for post injection assessments:

Step 1: If the safety and immunogenicity assessments are collected at scheduled visit, i.e. nominal scheduled visit, the data collected at scheduled visit will be used.

Step 2: If the safety and immunogenicity assessments are not collected at the scheduled visit, assessments collected at unscheduled visit will be used using the analysis visit windows described in Table 3 below.

If a subject has multiple assessments within the same analysis visit, the following rule will be used:

- If multiple assessments occur within a given analysis visit, the assessment closest to the target study day will be used.
- If there are 2 or more assessments equal distance to the target study day, the last assessment will be used.

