Day 29 (Month 1)	29 (Date of Second Injection)
Day 29 (Month 1)	29 (Date of Second Injection)
Day 57 (Month 2)	57
Day 149 (Month 2)	149 (Date of Booster Dose)
Day 149 (Month 2)	149 (Date of Booster Dose)

Day 177	177	[164, 253]
Day 329	329	[254, 422]
Day 514	514	$\geq 423$
Part 2 (For participants who do not receive booster dose)		
Day 1	1 (Date of First Injection)	$\leq 1$ , Pre-first-dose
Day 1	1 (Date of First Injection)	1, Post-first-dose
Day 29 (Month 1)	29 (Date of Second Injection)	[2, 43] Pre-second-dose
Day 29 (Month 1)	29 (Date of Second Injection)	[2, 43] Post-second-dose
Day 57 (Month 2)	57	[44, 133]
Day 209 (Month 7)	209	[134, 301]
Day 394 (Month 13)	394	$\geq 302$
Part 3 (For participants who receive dose 2)		
Day 1	1 (Date of First Injection)	$\leq 1$ , Pre-first-dose
Day 1	1 (Date of First Injection)	1, Post-first-dose
Day 29 (Month 1)	29	[2, 105]
Day 181 (Month 6)	181 (Date of Second Injection)	[106, 195] Pre-second-dose
Day 181 (Month 6)	181 (Date of Second Injection)	[106, 195] Post-second-dose
Day 209 (Month 7)	209	[196, 285]
Day 361 (Month 12)	361	$\geq 286$
Part 3 (For participants who receive a single dose)		
Day 1	1 (Date of First Injection)	$\leq 1$ , Pre-first-dose
Day 1	1 (Date of First Injection)	1, Post-first-dose
Day 29 (Month 1)	29	[2, 105]
Day 181 (Month 6)	181	$\geq 106$
Immunogenicity		
Part 1B, Part 1C-1 and Part 1C-2		
OL-Day 1	1 (Date of First Injection in Part 1B) relative to OL-Day 1	1, Pre-first-dose

OL-Day 57 (Month 2)	57 relative to OL-Day 1	≥44 and before BD-Day 1 for subject receiving BD
OL-Day 57 (Month 2)	57 relative to OL-Day 1	[44, 117] for subject declining BD
OL-Day 178 (Month 6)	178 relative to OL-Day 1	≥18 for subject declining BD
BD-Day 1	1 (Date of Injection in Part 1C-1, Part 1C-2) relative to BD-Day 1	≤1 and V[SIT is BD-Day 1
BD-Day 29 (Month 1)	29 relative to BD-Day 1	[2, 105]
BD-Day 181 (Month 6)	181 relative to BD-Day 1	[106, 271]
BD-Day 361 (Month 12)	361 relative to BD-Day 1	>272
Part 2 (For participants who receive booster dose)		
Day 1	1 (Date of First Injection)	1, Pre-first-dose
Day 29 (Month 1)	29 (Date of Second Injection)	[2, 43]
Day 57 (Month 2)	57	[44, 103]
Day 149 (Month 2)	149 (Date of Booster Dose)	[104, 163]
Day 177	177	[164, 253]
Day 329	329	[254, 422]
Day 514	514	≥423
Part 2 (For participants who do not receive booster dose)		
Day 1	1 (Date of First Injection)	1, Pre-first-dose
Day 29 (Month 1)	29 (Date of Second Injection)	[2, 43]

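### In Part 1C-1 the pre-booster titer may come from any earlier visit, so a missing BD-Day 1 titer is filled by Day 209 or Day 57, affecting the exploratory booster fold rise

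*SAP*

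**What the plan says.** All references are to the SAP for Parts 1B, 1C, 2 and 3 unless stated.

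- **Section 6.1, Baseline Value for Each Part:** for immunogenicity tests, "the pre-booster is defined as the most recent non-missing measurement (scheduled or unscheduled) collected before or on the date of booster dose".
- **Section 6.4.1, Sampling Plan:** the Part 1C-1 subset is tested at the "long-term timepoints (Day 1, Day 57, and Day 209) and subsequent booster dose phase timepoints (BD-Day 1 and BD-Day 29"). Older post-dose-2 titers therefore exist in the same participants.
- **Section 5.3, PP Immunogenicity Subset (Part 1C-1):** the only antibody result required is "Had BD-Day 29 Ab assessment for the analysis endpoint". No BD-Day 1 titer is needed. In Part 1A, by contrast, the PP Immunogenicity Subset needed a baseline titer (SAP for Part 1A, Section 5.4).
- **Appendix B, Table 3, Immunogenicity:** a titer counts as BD-Day 1 only if "≤1 and V[SIT is BD-Day 1" (the stray bracket is an extraction fault in the word VISIT). The appendix introduces its rules with "Safety and Immunogenicity Analysis will be summarized using the following analysis visit window for post injection assessments".
- **Section 3.2.4:** the exploratory endpoints are GM values on BD-Day 1 and at later booster visits.
- **Section 6.4.6:** the listed time points include one called Pre-booster, not BD-Day 1. Fold rise is taken at each time point over baseline "and post-booster timepoint over pre-dose 1 level and pre-booster level (Part 1C only"). The pre-booster value is also the reference for an optional seroresponse analysis and, if applicable, a covariate in an optional ANCOVA against boosted adults in P301.

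**The concern.** A fold rise after a booster is meant to compare the titer after the dose with the titer just before it. A rule that reaches back without limit can put a titer from months earlier in the denominator and still call it pre-booster. Antibody may have waned since then, or risen after an infection, and the carried value reflects neither.

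The SAP also leaves open which rule fills the Pre-booster time point in Section 6.4.6. Under Section 6.1, a Day 209 result may appear both as Day 209 and as Pre-booster in the same summary. Under the Table 3 window, the participant has no BD-Day 1 value. Two programmers could derive different numbers from this text. At stake are the pre-booster GM, the booster GMFR, the proportion with at least a 2-fold rise, the pre-booster-referenced seroresponse and the ANCOVA covariate.

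**Working it through.** **No plan figure to reproduce.** The SAP gives no missing rate for BD-Day 1 titers, no waning rate and no expected fold rise, so the size below rests on stated assumptions.

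**Step 1. Which titer is carried forward.** With BD-Day 1 missing, the latest earlier titer in the testing list is Day 209. Day 57 is reached only if Day 209 is missing as well, or if Day 209 and BD-Day 1 were one visit and that sample was lost. The Part 1C-1 schedule (SAP for Part 1A, Appendix G) places BD-D1 at D209 for the original mRNA-1273 group.

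**Step 2. How old it can be.**
- Day 57: 28 days after dose 2. The booster is at least 5 months (about 152 days) after dose 2. Gap at least 152 − 28 = 124 days.
- Day 209: the gap can be zero, but need not be. Boosters in the subset start on 27 December 2021 (Section 6.4.1). A participant who was at Day 57 on the Part 1A snapshot date of 08 May 2021 (Section 4.4) has a nominal Day 209 that is 209 − 57 = 152 days later, on 7 October 2021. That is 81 days before 27 December. How many subset members fit these dates is unknown.

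**Step 3. Ratio r of carried titer to true BD-Day 1 titer.** With half-life h, r = 2^(gap/h). Assumed h is 60 to 120 days.
- Day 209 carried 81 days: 2^(81/120) = 1.6 to 2^(81/60) = 2.5.
- Day 57 carried 124 days: 2^(124/120) = 2.05 to 2^(124/60) = 4.19.

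**Step 4. Effect on the GMFR.** The log GMFR is the mean of log(post) − log(pre). If a share m of participants has a denominator r times the true one, the mean falls by m·ln r, so reported GMFR / true GMFR = r^(−m).

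| Share carried, m | r = 0.5 | r = 1.5 | r = 2 | r = 4 |
|---|---|---|---|---|
| 2% | 1.014 | 0.992 | 0.986 | 0.973 |
| 5% | 1.035 | 0.980 | 0.966 | 0.933 |
| 10% | 1.072 | 0.960 | 0.933 | 0.871 |

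Of the 289 targeted participants, 5% is about 14. The r = 0.5 column stands for a titer that doubled after the carried sample, for example after infection; there the fold rise is overstated.

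**Step 5. One participant.** The error is the full factor r. A true 6-fold rise with r = 2 reads as 6/2 = 3-fold and fails the 4-fold seroresponse criterion.

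**Step 6. Where it does not reach.** The coprimary seroresponse is referenced to pre-Dose 1 (Sections 3.2.2 and 4.2.1.1). The coprimary GMR is an unadjusted difference of mean log titers (Section 6.4.3). The key secondary endpoints use the same methods (Section 6.4.4). None uses the pre-booster titer. In Part 1C-2 the schedule (SAP for Part 1A, Appendix H) has no immunogenicity draw before BD-D1, so there is no earlier scheduled titer to carry.

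**The case against.** The last value before dosing is a common baseline convention. Part 1A pairs a similar most-recent rule with a separate Day 1 window, and Appendix B describes itself as covering post-injection assessments. On that reading Section 6.1 derives the pre-booster value, the window table serves by-visit summaries, and the GM and the GMFR in Section 6.4.6 share one rule because both use the term pre-booster. This stands to the extent that a reader who infers an outright contradiction goes too far: the two rules can coexist. They are still unreconciled, since Table 3 contains a pre-dose BD-Day 1 row and Section 3.2.4 names BD-Day 1 as the endpoint time point.

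The rule may also rescue a valid booster-day sample filed under Day 209 when visits are combined. This is largely answered by Section 4.1.1.3 of the SAP for Part 1A, under which a visit coinciding with BD-Day 1 follows the Part 1C-1 schedule. Tying the definition to the booster date rather than the visit label meets it fully.

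Three stronger readings are tempting and not supported:
- *The post-dose-2 peak is the usual substitute.* Day 57 is used only when no Day 209 titer is available.
- *An illness-visit titer may be carried.* The schedules describe respiratory samples and clinical evaluations at illness visits. Blood is drawn at the Part 1A convalescent visit, but the subset's listed testing does not include it.
- *The booster response is always understated.* That needs waning alone. It is the expected direction in the pre-booster negative set, but the full PP set, analysed by pre-booster status, includes positives.

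**Conclusion.** The point holds as a minor one. Followed as written, Section 6.1 gives a participant without a BD-Day 1 titer an out-of-date denominator, and the SAP does not say whether Pre-booster and BD-Day 1 are the same time point.

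The effect on the group GMFR is probably a few percent: 2% to 7% too low with 5% of titers carried and r from 1.5 to 4, and 3.5% too high if r = 0.5. Approaching 13% needs 10% carried, all from Day 57, at the fastest assumed waning. Half-life and missingness are assumptions; the SAP supports neither, and nothing in it suggests that the BD-Day 1 draw is often missed.

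A reader might infer that the booster noninferiority conclusion is at risk. It is not. The effect is confined to exploratory analyses in Section 6.4.6, some of them optional, and the target of 289 is untouched.

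**What to change.** In Section 6.1, define the Part 1C-1 pre-booster titer for the GM, the GMFR and fold-rise proportions, the pre-booster-referenced seroresponse and the ANCOVA covariate as the pre-dose sample taken on the booster date, whatever its visit label, or within a short stated interval before it. If there is no such sample, treat the value as missing for those analyses. State in Section 6.4.6 that Pre-booster means this sample, and word the BD-Day 1 immunogenicity row of Appendix B to match.

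The cost is a sentence in Section 6.1 and two matching edits. A few participants drop out of the pre-booster-referenced exploratory summaries, which are then unbiased only if missing BD-Day 1 titers are unrelated to response. Sample size and confirmatory testing do not change.
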